### **5.4 Additional analyses/exploratory analysis**

No other analyses were planned.

### **5.5 Harms & Adverse events**

The number (percentage) of patients experiencing each AE/SAE will be presented for each treatment arm categorised by severity (across follow-up time) (Ioannidis *et al.*, 2004). For each participant, only the maximum severity experienced of each type of AE will be displayed. The number (percentage) of occurrences of each AE/SAE will also be presented for each treatment arm. No formal statistical testing will be undertaken (Phillips, Sauzet and Cornelius, 2020).

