**Study Design:**

This optimisation study uses a two-arm, parallel-group, randomised controlled trial. The study's randomisation method allocates participants using a 1:1 overall ratio to one of two arms:

Immediate intervention arm = immediate access to the brief digital imagery-competing task intervention plus symptom monitoring for 4 weeks

Delayed intervention arm = usual care for 4 weeks followed by access to the intervention plus symptom monitoring for 4 weeks

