## 8.2 Safety Reporting Procedures

No major risks are expected in association with any part of the study methodology or intervention. The brief behavioural intervention is non-invasive, minimally distressing, and no study-related adverse events have been reported in any previous trials or studies testing the intervention. In this trial, any adverse events will be self-reported at 4-week and 8-week assessment. In the event that any adverse events are reported by participants, this will be reviewed by the Chief Investigator in the first instance, and with a clinical colleague in the research team as necessary. If a serious adverse event is identified (i.e. meeting the definition in section 8.1.2 above), this will be reported to the REC (in line with section 8.2.2 below).

As in any study, and unrelated to the study methodology, there may be participants for whom significant risk to themselves or others becomes apparent during the study period, e.g. through spontaneously reporting suicidal intent during contact with the research team or in open-response questionnaire items. In these cases, the research team will encourage the participant to seek help e.g. contact their GP or other relevant healthcare provider. Any such instances will be discussed within the research team and recorded appropriately.

At the end of the study, all participants will be sent information about access to mental health support, such as the NHS/Every Mind Matters website, the Intensive Care Society Wellbeing Hub webpage and advice to contact their GP/occupational health team.

Additionally, if at any point during the study the participant reveals information that may suggest professional malpractice, they will be encouraged by the researcher to report this to their Hospital's Freedom To Speak Up (FTSU) Guardian and/or to follow their Trust Whistleblowing Policy.

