# 1. Introduction

This document seeks to follow the template and guidelines proposed by Gamble et al. (2017) when analysing and reporting the main results from the current study titled “A randomised optimisation study of a brief digital imagery-competing task intervention to support NHS ICU staff experiencing intrusive memories of traumatic events from working in the COVID-19 pandemic”, which is shorted as “A brief GAmesplay Intervention for NHS ICU Staff affected by COVID-19 trauma (GAINS Study)”. These analyses will explore the efficacy and safety of a brief digital imagery-competing task intervention in comparison with usual care and will be included in the clinical study report, to inform a future definitive clinical trial design.

The purpose of the plan is to:

- Ensure that the analysis is appropriate for the aims of the trial, reflects good statistical practice, and that interpretation of a priori and post hoc analyses respectively is appropriate.
- Explain in detail how the data will be handled and analysed to enable others to perform or replicate these analyses.

Bayesian and frequentist analyses were proposed for statistical inference in this study. The Bayesian approach will be used throughout data collection to inform on study design and the details can be found in a separate file named “*P1V\_GAINS\_IN01 Optimisation SAP.pdf*”. The present document (the “D-SAP”) will present the details for all frequentist analysis in line with the analysis specified in study protocol.

Additional exploratory or auxiliary analyses of data not specified in the protocol may be included in this analysis plan. This analysis plan will be made available in a public platform before the trial database is locked for the final analysis. Additional analyses suggested by reviewers or editors will be performed if considered appropriate. This will be documented in a file note. Amendments to the statistical analysis plan will be described and justified in the final report of the trial and where appropriate in publications arising from the analysis.

Other health economic and qualitative analysis plans are beyond the scope of this document. Note the quantitative part of the Intervention Feedback questionnaire will be analysed (See Section 5 for details).

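### The adverse event tables in SAP 5.5 do not separate the randomised period (to week 4) from weeks 5–8, when the delayed arm also has the intervention

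*SAP*

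**What the plan says.** SAP 5.5 plans three displays.

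- Participants: "The number (percentage) of patients experiencing each AE/SAE will be presented for each treatment arm categorised by severity (across follow-up time").
- Grading: "For each participant, only the maximum severity experienced of each type of AE will be displayed".
- Events: "The number (percentage) of occurrences of each AE/SAE will also be presented for each treatment arm".

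It adds "No formal statistical testing will be undertaken", so all of this is descriptive. The section sets no cut at week 4 and defines no period on or off the intervention.

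Three other statements bear on it. SAP section 1 gives the purpose: "These analyses will explore the efficacy and safety of a brief digital imagery-competing task intervention in comparison with usual care". The protocol synopsis, under Study Design, fixes the exposure: "Delayed intervention arm = usual care for 4 weeks followed by access to the intervention plus symptom monitoring for 4 weeks". Protocol 8.2 fixes the collection: "any adverse events will be self-reported at 4-week and 8-week assessment".

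The protocol is not consistent on how long the immediate arm keeps access. The synopsis (Outline of Study) and sections 5.6 and 5.7.1 give 4 weeks, to Day 28. Section 3.1 continues access for the rest of the study period, section 3.2 gives 8 weeks, and section 5.7.4 allows optional use in weeks 5 to 7.

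**The concern.** Usual care exists as a randomised comparator only until week 4. After that the delayed arm starts the intervention, and any difference between arms no longer contrasts the intervention with usual care. The SAP respects this for efficacy, where the primary comparison is at week 4, but it sets no matching limit for harms.

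If the tables run to week 8, an excess of events caused by the intervention enters both arms, early in one and late in the other. The main harms display could then show similar arms when weeks 1–4 did not. The SAP says its results will inform a definitive trial, so the reader of that display needs the controlled comparison.

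**Working it through.** **Step 1: what the time phrase means.** SAP 5.2.1 uses a near-identical phrase, in the plural and for measures collected repeatedly, to mean a summary at each assessment. SAP 5.2.6 gives 4 and 8 weeks as examples. Read that way, 5.5 would yield a week-4 table by arm. Three features of 5.5 point to pooling instead: the singular noun, a single worst grade per participant and event type with no period named, and an occurrence count with no time wording at all. Pooling is the more natural reading but is not stated. For occurrences, no reading of the text supplies a split.

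**Step 2: inputs.** The documents give no adverse event rates, so there is no figure to reproduce and the rates below are assumptions.

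- b: risk of an event per 4 weeks off the intervention, 5–20%.
- e: added risk in a 4-week block with access, 5–15 percentage points.
- Blocks are independent, and the excess is the same in each block with access.
- 75 participants per arm, the planned maximum (protocol synopsis).

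**Step 3: formulas.**

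- Weeks 1–4: immediate b + e, delayed b.
- Pooled, 4 weeks' access in each arm: both arms 1 − (1 − b − e)(1 − b). The difference is 0 for every b and e.
- Pooled, immediate arm with access to week 8: immediate 1 − (1 − b − e)², delayed 1 − (1 − b)(1 − b − e). The difference is e(1 − b − e).

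**Step 4: results (immediate vs delayed).**

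| b, e | Weeks 1–4 | Pooled, 4 weeks each | Pooled, immediate arm 8 weeks |
|---|---|---|---|
| 10%, 10 points | 20% vs 10% | 28% vs 28% | 36% vs 28% |
| 5%, 10 points | 15% vs 5% | 19.25% vs 19.25% | 27.75% vs 19.25% |
| 20%, 5 points | 25% vs 20% | 40% vs 40% | 43.75% vs 40% |
| 5%, 15 points | 20% vs 5% | 24% vs 24% | 36% vs 24% |

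For the first row, 1 − 0.8 × 0.9 = 0.28 and 1 − 0.8² = 0.36. With 75 per arm, the expected counts are 15 vs 7.5 in weeks 1–4, then 21 vs 21 or 27 vs 21 when pooled. The risk ratio falls from 2.0 to 1.0 or to 0.36/0.28 = 1.29.

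Over the whole assumed range, weeks 1–4 show differences of 5–15 points and risk ratios of 1.25–4.0. Pooled with 8 weeks' access in the immediate arm, these become 3.75–12 points and 1.09–1.50. If optional use in weeks 5–8 carries less than the full excess, the pooled difference lies between that case and zero.

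**Step 5: after a split at week 4.** The first table returns the weeks 1–4 column, with the excess e undiluted.

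**The case against.** The strongest reply is that 5.5 should be read by the SAP's own usage in 5.2.1 and 5.2.6. Adverse events are collected at weeks 4 and 8, so the planned tables would already include a week-4 comparison by arm. That reading is possible, and a reader who infers that the SAP states pooling goes beyond the text. The occurrence count still has no time wording. The SAP also aims to let others replicate its analyses, so this choice should not be left open.

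A reader might also infer that a worst-grade rule makes sense only in a table pooled to week 8. The documents do not support that. A participant can report the same type of event more than once within 4 weeks, so the rule works equally well within a period. Any pooling comes from the sentence before it; the rule only removes timing if the table is pooled.

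Third, part of the comparison is planned elsewhere. The Changes to Health and Work questionnaire (SAP Table 2) has a yes/no item on untoward medical occurrences at weeks 4 and 8, close to the adverse event definition in Protocol 8.1.1. Under SAP 5.2.1 it is summarised by arm and time. This stands as partial mitigation, but the scored item carries neither type nor severity.

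Finally, events may be few. Protocol 1.3.2 and 8.2 report no study-related adverse events in earlier studies of the intervention. The Chief Investigator reviews reported events and the Data Monitoring Committee advises on safety. So the plan does not leave harms unreviewed; the weakness is in how they are displayed.

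**Conclusion.** The point holds in a limited form. SAP 5.5 does not guarantee the one randomised safety comparison with usual care that the design allows, and on its most natural reading it gives a table pooled to week 8 instead. It should be clarified before the tables are produced.

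The size depends on assumed rates and on the length of access. A reader might infer that the comparison is bound to cancel out. Complete cancellation, 28% vs 28% in the example, requires access in the immediate arm to end at Day 28, with independent blocks and the same excess in both arms. Protocol 3.1, 3.2 and 5.7.4 imply continued access, which gives dilution (36% vs 28%). The passages on access must be reconciled, but pooling distorts the comparison either way.

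Because no adverse event test is planned, the risk is a misleading description, not an invalid p-value. The primary analysis is unaffected.

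**What to change.** In SAP 5.5, present participants with each AE/SAE, worst grade and occurrences by arm, separately for two periods:

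1. Day 1 to the week-4 assessment, as the randomised comparison with usual care. In the delayed arm this period should end no later than the first guided session. Protocol Appendix 1 allows week-4 measures up to 7 days late, and that session can fall from Day 29 to 7 days later, so a cut at the assessment alone could admit days after the intervention has started. Applying this limit to late assessments relies on event onset dates.
2. From then to week 8, labelled as both arms exposed.

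Two details need stating. Events between consent and Day 1 should be listed separately, because Protocol 8.2.1 records events from consent. Period 1 should use only sources given to both arms at week 4. The feedback questionnaire also asks about adverse events (Protocol 5.7.7), but only the immediate arm completes it at that time (SAP Table 2).

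The protocol's passages on length of access should be reconciled so that period 2 can be described correctly. A further table of the first 4 weeks after the first guided session, arms combined, is optional and has no comparator.

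The cost is SAP wording, one extra descriptive table and smaller counts in each table. No new collection point is needed, since events are already reported at weeks 4 and 8.

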### **5.6 Statistical software**

For all descriptive statistics and modelling for all outcomes, Stata and R, will be used. The scripts for the final analysis will be made available on the Open Science Framework to reviewers prior to publication and be made publicly available after the main paper(s) have been published. All the software will use the latest version available in University of Nottingham (UoN) when study data is ready for analysis. All the data will be stored in UoN secure server and analysed in computers located in

UoN. All the data and analytic code will be archived as per instruction from study PI [name] & Sponsor [name] who will be the data custodian for this study.

